4.11.6 Adverse event of special interest (AESI)

AESI are defined in the protocol as follows and collected in the eCRF using a specific question.

- Cases of an elevated ALT or AST in combination with either an elevated bilirubin or clinical jaundice.
- Suspected transmission of an infectious agent by the study treatment.

The following listings will be provided:

• A by-subject listing of all AESI.

4.11.5 Selected Adverse Events

Selected adverse events are

- non serious infections that require treatments with IV antibiotic, antifungal, antiviral
- opportunistic infections defined as per basket with PO antibiotic, antifungal, antiviral injection-related reaction (IRR; an AE which occurs within 24 hours after study treatment injection except where the event is not considered an allergic reaction.

The following summary tables and listings will be provided:

• A by-subject listing for non-serious infection (SOC: Infections and infestations) medicated by IV treatment antibiotic, antifungal, antiviral.

TP-GDO-WW-016-01 Confidential Version 7.0
Effective Date: 28Aug13 Version Date: 28NOV2018
Related to: SOP-GDO-WW-019 Page 29 of 60

 A by-subject listing for opportunistic infection (defined by MedDRA basket in Appendix 7.4) medicated by PO treatment antibiotic, antifungal, antiviral.

4.11.7 Infections, Serious Infection,

Serious adverse event in "SOC: Infections and infestations" will be summarized.

Opportunistic infections are defined from all adverse events by MedDRA basket in Appendix 7.4 and reported as described in section 4.11.5 selected adverse events... Serious infection will be provided per 100 patient-years by treatment group during the double-blind period. The patient-years will be based on the double-blind period for safety analysis (see section 4.2). The rate per 100 patient-years by treatment group (along with the 95% CI) will be calculated for serious infections.

The number of serious infections per 100 patient-years is calculated as:

Total number of serious infections / Total number of patient-years ×100

The 95% CI for the number of serious infections per 100 patient-years is calculated as follows:

Exact lower 95% confidence limit = chisq (p = 0.025, df = 2 Y) / (2 T)

Exact upper 95% confidence limit = chisq [p = 0.975, df = 2(Y + 1)] / (2T)

where Y is the total number of serious infections, T is total number of patient-years at risk and chisq (p,df) is the quantile of the upper tail probability of the X2 distribution on df degrees of freedom. This approach has the advantage of providing an estimate for the upper 95% confidence limit even when the total number of serious infections is zero.

The following summary tables will be provided.

- A summary of serious infection by SOC and PT.
- Rates of serious infections by 100 patient-years.
- A by-subject listing of Infections.
- A by-subject listing of Opportunistic Infections.

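### The 95% CI limits for serious infections per 100 patient-years omit the factor 100 used in the estimate, and the chi-square quantile is defined on the wrong tail

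*SAP*

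**What the plan says.** SAP 4.11.7 (Infections, Serious Infection) plans a rate of serious infections per 100 patient-years, by treatment group, for the double-blind period. It defines:

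- the estimate: "Total number of serious infections / Total number of patient-years ×100";
- the scale of the interval: "The 95% CI for the number of serious infections per 100 patient-years is calculated as follows";
- the lower limit: "Exact lower 95% confidence limit = chisq (p = 0.025, df = 2 Y) / (2 T");
- the upper limit: "Exact upper 95% confidence limit = chisq [p = 0.975, df = 2(Y + 1)] / (2T");
- the quantile function used in both limits: "chisq (p,df) is the quantile of the upper tail probability of the X2 distribution on df degrees of freedom";
- the event count and the exposure: "where Y is the total number of serious infections, T is total number of patient-years at risk".

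Patient-years come from the double-blind safety period defined in SAP 4.2. The section adds that the method still gives an upper limit when no serious infection occurs. Nothing elsewhere in the SAP corrects or restates these formulas; Appendix 7.1 gives code only for time to first relapse, pain and fatigue.

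**The concern.** The estimate carries a factor of 100 and the limits do not, although both are described as being per 100 patient-years. A table programmed from this text would show a rate with a confidence interval lying wholly below it. Separately, the probabilities 0.025 (lower limit) and 0.975 (upper limit) are right only for a lower-tail quantile, while the text defines an upper-tail one.

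Serious infection is the only safety outcome for which the SAP plans a patient-year rate with a CI, and it heads the list of risks in Protocol 5.1.1. The zero-event case matters most. There the upper limit is the only information the interval carries, and an upper limit 100 times too small overstates safety without looking wrong.

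**Working it through.** The SAP gives formulas but no worked rate, so there is no stated figure to reproduce. The inputs are the definitions in SAP 4.11.7. Values of Y and T below are assumed for illustration; the ratios in step 2 do not depend on T.

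**1. What the written limits estimate.** With lower-tail quantiles, chisq(0.025, 2Y)/2 and chisq(0.975, 2(Y+1))/2 are the exact Poisson limits for the expected count. Dividing by T in patient-years gives limits per one patient-year. Check at Y = 3, T = 100: the quantiles are 1.237 (6 df) and 17.535 (8 df). The limits are 1.237/200 = 0.0062 and 17.535/200 = 0.0877 per patient-year, and each leaves a Poisson tail probability of 0.0250. The degrees of freedom and the p values are therefore correct for a lower-tail quantile, and only the scale is wrong.

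**2. Limit against estimate.** T cancels:

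upper limit / estimate = [chisq(0.975, 2Y+2)/(2T)] / [100Y/T] = chisq(0.975, 2Y+2)/(200Y)

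| Y | chisq(0.975, 2Y+2) | 200Y | Ratio |
|---|---|---|---|
| 1 | 11.143 | 200 | 0.0557 |
| 3 | 17.535 | 600 | 0.0292 |
| 5 | 23.337 | 1000 | 0.0233 |
| 10 | 36.781 | 2000 | 0.0184 |

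Over Y = 1 to 2000 the largest ratio is 0.0557, at Y = 1, so the estimate is always above the written upper limit.

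**3. Size on the reported scale (T = 100 assumed, lower-tail quantiles).**

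| Y | Estimate per 100 PY | Limits as written | Limits × 100 |
|---|---|---|---|
| 0 | 0 | 0 to 0.037 | 0 to 3.69 |
| 1 | 1.0 | 0.0003 to 0.056 | 0.025 to 5.57 |
| 3 | 3.0 | 0.0062 to 0.088 | 0.62 to 8.77 |
| 5 | 5.0 | 0.016 to 0.117 | 1.62 to 11.67 |
| 10 | 10.0 | 0.048 to 0.184 | 4.80 to 18.39 |

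The lower limit at Y = 0 is taken as 0, because the formula then has 0 degrees of freedom. For true rates of 2, 5 and 10 per 100 patient-years and T = 50, 100 and 150, exact coverage is 95.8% to 98.8% with the factor 100 and effectively zero without it.

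**4. Zero events in the placebo arm.** The documents give no patient-year total, so I assume T = 15 to 25. The corrected upper limit is 100 × 7.378/(2T): 24.6 at T = 15 and 14.8 at T = 25. At T = 21 it is 17.6, where the written formula gives 0.176.

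**5. Tail definition.** Taking the SAP's upper-tail definition literally at Y = 3, T = 100, the lower limit is 14.449/200 = 0.072 and the upper limit is 2.180/200 = 0.011, which is reversed. The reversal occurs for every Y from 1 to 2000, and multiplying by 100 does not cure it.

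**6. Other readings.** T in hundreds of patient-years would repair the scale, but the SAP defines T as total patient-years. Reading the estimate as Y/(100T) would not be a rate per 100 patient-years, and the written lower limit would then exceed the estimate (2.53 times at Y = 1, 32.47 times at Y = 5).

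**The case against.** Apart from the scale and the tail label, these are the standard exact Poisson limits, and the text makes the intended scale plain. A competent programmer would probably rescale, because an interval that excludes its own estimate stands out in a table. The p values also show that cumulative quantiles were meant, so reversed limits are unlikely to be delivered. The rate is descriptive. A factor of 100 lost when the text was read from PDF cannot be wholly excluded.

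Most of this bears on consequence and supports a low severity. It does not make the stated rule correct. The mismatch is visible only when Y is at least 1; with no events nothing looks wrong. SAP 4.1 requires outputs to be independently checked, and the SAP formula is the natural reference for that check. Text loss is unlikely: the factor survives in the estimate line, both limit lines read as complete, and loss of a factor would not explain the tail wording. Leaving the lower limit unstated at Y = 0 is only untidy, since 0 is the sole sensible value.

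**Conclusion.** The concern holds: the interval is wrong as written. Both limits are 100 times too small for a rate per 100 patient-years, and for every Y from 1 to 2000 the written interval excludes its own estimate at any T. The tail definition is also wrong but secondary, because the p values reveal the intent. The ratios rest only on the SAP's own definitions; the intervals at particular values of T are illustrations. Severity is minor: one descriptive safety rate is affected, and the primary analysis, the key secondary analyses and the gatekeeping do not use it. The documents do not show whether any delivered table carries the error.

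**What to change.** Replace the formulas in SAP 4.11.7 with:

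- lower limit = 100 × chisq(0.025, 2Y)/(2T), set to 0 when Y = 0;
- upper limit = 100 × chisq(0.975, 2(Y+1))/(2T);
- chisq(p, df) = the value with cumulative (lower-tail) probability p on df degrees of freedom.

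Check the program against one worked case: Y = 5, T = 150 should give 3.33 (1.08 to 7.78) per 100 patient-years. Protocol 1.3 states that the double-blind period is complete, so apply the same check to the serious-infection table already produced, including any arm with zero events. The cost is a few lines of SAP text and one program check; no analysis choice changes.

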4.11.8 Anaphylaxis

Anaphylaxis is defined by MedDRA SMQ "Anaphylactic reaction - Narrow" and will be listed

A by-subject listing of Anaphylaxis.

TP-GDO-WW-016-01 Effective Date: 28Aug13 Related to: SOP-GDO-WW-019

Page 30 of 60

4.11.9 IRR and ISR

IRR in CRF selected AE (IRR) page will be summarized. ISRs flagged as "Injection site reaction" in CRF selected AE (IRR) or general AE page will be summarized. The following summary tables will be provided:

- A summary of IRR
- A summary of ISRs by SOC and PT.
- A by-subject listing of all IRRs.
- A by-subject listing of all ISRs.

4.11.10 Clinical Laboratory Evaluation

For continuous laboratory measurements including hematology, clinical chemistry, and urinalysis, summary using descriptive statistics of the actual values and their change from baseline will be presented by treatment group at each visit. The laboratory tests to be performed are presented in Table 4-4.

When analyzing categorical data, the number and percentage of subjects in each category will be presented. In addition, shift tables may be used to evaluate the number and percentage of subjects having a different post-baseline status when compared to their baseline status.

A subject data listing will be provided for all laboratory data. Values outside the normal range will be flagged within the listing. A subject data listing will also be provided for all treatment emergent marked laboratory abnormalities (see Appendix 7.5).

The following summaries, listings and figures will be provided: by treatment group

- A summary of each laboratory parameter in Table 4-4 and change from baseline will be provided by visit.
- A shift table based on the normal range for each laboratory parameter will be presented by double-blind period endpoint value relative to baseline by treatment group.
- A by-subject listing of laboratory parameters.

Table 4-4 Laboratory measurements

Hematology	Clinical chemistry	Urinalysis	Complement
Hematocrit Hemoglobin International normalized ratio (INR) Platelet count Red blood cell (RBC) count WBC count	Sodium Potassium Chloride Calcium Phosphorous Ferritin Blood urea nitrogen (BUN) Creatinine	Glucose Protein Urinary occult blood Urobilinogen	Complement tests (C3, C4 and CH50)

TP-GDO-WW-016-01 Effective Date: 28Aug13 Related to: SOP-GDO-WW-019 Confidential Version 7.0 Version Date: 28NOV2018

Page 31 of 60

Absolute differential count (neutrophils, eosinophils, lymphocytes, monocytes, basophils, other cells)	Total bilirubin Fibrinogen Total serum protein Albumin ALT AST Alkaline phosphatase Gamma-glutamyl transpeptidase (γ-	
	Gamma-glutamyl	
	GTP) Lactate	
	dehydrogenase	
	(LDH)	
	Total cholesterol	
	Low density	
	lipoprotein	
	cholesterol (LDL)	
	High density	
	lipoprotein	
	Cholesterol (HDL)	
	Triglycerides Creatine kinase	
	(CK)	
	Uric acid	

4.11.11 AST and ALT:

AST and ALT will be categorized into four group (>3-5 xULN, 6-10 xULN, 11-20 xULN and 21- xULN) based on maximum post-baseline levels within baseline and post-baseline respectively for each test by maximum post-baseline levels for total bilirubin and alkaline phosphatase (total bilirubin <= 2xULN, total bilirubin > 2xULN, total bilirubin > 2xULN and alkaline phosphatase < 2xULN, total bilirubin > 2xULN and alkaline phosphatase <= 5xULN). The denominator is the number of subjects with any valid assessment at baseline and post-baseline respectively. Subjects with AST or ALT results fulfilling criteria for more than one category are counted only once, in the category indicating the highest elevation level within baseline and post-baseline.

Summary of AST and ALT Results.

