5.1.1.2 Neutropenia and Potential Risk of Infection

Reversible neutropenia was reported in 1 of 33 patients with rheumatoid arthritis in the Phase I multiple dose study (SA-105JP).

In the completed double-blind period of the Phase 3 studies, decreases in neutrophil counts have occurred following treatment with satralizumab, which was not associated

with serious infections. The majority of neutrophil decreases were transient or intermittent.

Patients with a low neutrophil count $<2 \times 10^3/\mu\text{L}$ will be excluded from this study.

Caution should be exercised in patients with a low neutrophil count and appropriate measures (such as interruption of satralizumab) should be considered if neutropenia persists.

Recommended dose interruption based on ANC results is shown in [Table 2](#).

Table 2 Neutropenia Risk Mitigation

ANC (/uL)	Action
>1,000	Maintain dose
500 – 1,000	
• If neutropenia persists, satralizumab should be interrupted until ANC is above 1,000/uL.• If ANC is under 1,000/uL at the previous laboratory test, ANC must be checked before treatment with the satralizumab (e.g., ANC test at site).
<500	Satralizumab should be discontinued.

ANC = absolute neutrophil count.

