6.6 SAFETY ANALYSES

All safety analyses will be performed on the SAF. Safety variables to be assessed are AEs, AESIs, SAEs, IRRs, injection site reactions, patient withdrawals due to AEs, change in 12-lead ECGs, measurements of laboratory parameters, and vital signs (including body weight).

Summary tables for number and percentage of patients with adverse drug reactions which AEs related to study treatment will be tabulated.

Adverse events will be summarized by SOC and preferred term based on Medical Dictionary for Regulatory Activities (MedDRA) coding, and grade of severity. In addition, the incidence of AEs leading to withdrawal from treatment and SAEs will be tabulated.

Laboratory values (including hematology, blood chemistry, and urinalysis), frequencies of laboratory abnormalities, vital signs (temperature, SBP, DBP and pulse rate), physical examination 12-lead ECG, and suicidality (C-SSRS) will be summarized. Measurement and change from Baseline in continuous laboratory parameters (hematology, clinical chemistry, and urinalysis), continuous ECG, vital signs (blood pressures and pulse rate), and body weight will be summarized using descriptive statistics. When analyzing categorical data, the number and percentage of patients in each category will be presented. In addition, shift tables may be used to evaluate the number and percentage of patients having a different post-baseline status when compared to their baseline status. Numbers of patients who meet the marked abnormality criteria will also be presented.

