7.5 Laboratory Data Conversion and Transformation Rules

• Conversion to Système International (SI) Units

Laboratory data should be stored on the database in the units in which they were originally delivered by the laboratory.

For analysis and reporting purposes, the data will be converted to SI units to allow the comparison of data delivered in different original units.

Results that include inequality sign will be converted into a numeric form removing inequality sign.

TP-GDO-WW-016-01 Confidential Version 7.0 Effective Date: 28Aug13 Version Date: 28NOV2018 Related to: SOP-GDO-WW-019

Page 56 of 60

Results that cannot be converted into an expected numeric form nor interpreted, such as alphabetic entries like "adequate", will usually not be further processed, but displayed in patient listings.

Marked Laboratory Abnormalities

For each laboratory test, a Marked Abnormality Range has been defined. A value outside of this range is considered to be potentially clinically relevant. This Marked Abnormality Range is wider than the Reference Range.

In addition, for each laboratory test, a percentage change, as an increase and/or decrease, has been defined which represents a clinically relevant change from baseline.

A Marked Abnormality is therefore defined as a test result:

which is outside of the Marked Abnormality Range, and which also represents a clinically relevant change from baseline of at least the designated amount during or within 30 days after end of trial treatment.

Baseline is taken as the last valid value before starting treatment. If no baseline is available, the midpoint of the Reference Range will be substituted for processing purposes for determination of Marked Abnormalities.

For urinalysis a missing baseline value will be replaced by 0 (zero).

NOTE: For calculating means and mean changes over time, missing values will not be included. If no baseline is available, no change from baseline will be calculated.

Values above and below the Reference Range are flagged on the listing by H and L. respectively. Marked Abnormalities are flagged by HH or LL.

Reference Ranges

Related to: SOP-GDO-WW-019

TP-GDO-WW-016-01 Confidential Version 7.0 Effective Date: 28Aug13 Version Date: 28NOV2018

Page 57 of 60

Laboratory Test Class	Laboratory Test	SI Unit	Reference Range [1,2]	Marked Abnormality Range	Direction of Change	Relevant Change from Baseline

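### No laboratory table committed to in SAP 4.11.10 counts, by arm, the patients who ever had low neutrophils or platelets, although Protocol 6.6 promises a count of marked abnormalities

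*SAP*

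**What the plan says.** SAP 4.11.10 commits to three kinds of laboratory output: descriptive statistics by visit, a "shift table based on the normal range for each laboratory parameter will be presented by double-blind period endpoint value relative to baseline", and listings. It does not say what the endpoint value is. Beyond that, "shift tables may be used to evaluate the number and percentage of subjects having a different post-baseline status" is optional wording with no rule for which post-baseline value to take. Marked abnormalities, defined in Appendix 7.5, receive a by-subject listing and no table.

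Protocol 6.6 states that "frequencies of laboratory abnormalities" will be summarized and that "Numbers of patients who meet the marked abnormality criteria will also be presented".

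Neutropenia and thrombocytopenia are named in Protocol 5.1.1 among the risks needing a management plan, and Tables 2 and 3 attach interruption and discontinuation levels to them. Protocol 5.1.1.2 reports from the completed double-blind periods: "The majority of neutrophil decreases were transient or intermittent".

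For AST and ALT, by contrast, SAP 4.11.11 classifies patients "based on maximum post-baseline levels".

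**The concern.** For a decrease that comes and goes, the natural safety question is how many patients in each arm ever reached a low value. A shift to a single end-of-period value does not answer it, because a patient who dipped and recovered is shown as unchanged. A listing contains the information but leaves the reader to count it.

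Two things are at stake. The SAP delivers less than the protocol promises on marked abnormalities. And for two parameters to which the protocol attaches dosing rules, a reassuring endpoint shift table could be produced while a larger number of patients on satralizumab had a low count at some point.

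**Working it through.** **Which planned outputs count patients who were ever low?**

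| SAP output | Section | Counts patients ever low in neutrophils or platelets? |
|---|---|---|
| By-visit mean, SD, median, minimum, maximum | 4.2, 4.11.10 | No. The minimum is one value per arm and visit, not a number of patients; unscheduled, out-of-window-dose and relapse visits are left out |
| Normal-range shift to endpoint value | 4.11.10 | Only patients whose endpoint value is itself low |
| Further shift tables | 4.11.10 | Optional, no worst-value rule |
| Marked abnormalities | 4.11.10, Appendix 7.5 | Listing only |
| AST/ALT by maximum value | 4.11.11 | Not applied to these parameters |
| AE tables, including AEs leading to interruption or discontinuation | 4.11.3 | Only low values recorded as AEs |

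The last row is only a partial substitute. Under Protocol 5.3.5.4 a laboratory result is an AE if it is symptomatic, changes study treatment, leads to an intervention or a change in other therapy, or is judged clinically significant. In Table 2 the 500–1,000/µL band calls for interruption only if the neutropenia persists, so a single asymptomatic value in that band need not become an AE.

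**How much could an endpoint shift table miss?** The documents give no figure to reproduce, so this is an illustration. Assumptions: the endpoint value is the last value; a patient has one low episode covering L consecutive scheduled draws; its first low draw is equally likely to be any of the K draws. The last draw is then low with probability L/K.

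Protocol Table 6 schedules post-baseline laboratory tests at Weeks 2, 4, 8, 12, 16, 20, 24, 28, 32, 36, 40, 44 and 48, so K = 13:

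- L = 1: 1/13 = 7.7%
- L = 2: 2/13 = 15.4%
- L = 3: 3/13 = 23.1%

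On these assumptions the table would miss about 77% (100 − 23.1) to 92% (100 − 7.7) of affected patients. Follow-up varies, since patients leave the double-blind period at relapse or stay beyond Week 48. With 7 draws (to Week 24) the range is 1/7 = 14% to 3/7 = 43%. With 25 draws (13 plus 12 four-weekly draws to Week 96) it is 1/25 = 4% to 3/25 = 12%.

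**Would the promised count be enough by itself?** The limits differ:

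| | Reference lower limit (Appendix 7.5) | Marked-abnormality lower limit (Appendix 7.5) | Protocol Table 2/3 levels |
|---|---|---|---|
| Neutrophils | 1.80 × 10⁹/L = 1,800/µL | 1.50 × 10⁹/L = 1,500/µL, with a fall of at least 20% | 1,000 and 500/µL |
| Platelets | 150 × 10⁹/L = 150,000/µL | 100 × 10⁹/L = 100,000/µL, with a fall of at least 30% | 75,000 and 50,000/µL |

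Neither a normal-range shift nor a marked-abnormality count separates patients who crossed the Table 2 and 3 levels from those who did not.

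**The case against.** The strongest reply is that nothing has been withdrawn. The SAP is to be read together with the protocol, Protocol 6.6 still commits to the count, every out-of-range value is flagged, and in about 90 patients the listing of marked abnormalities can be counted by hand. This stands as far as it goes. A reader might infer that the trial cannot report these counts by arm. The documents do not support that: the data are collected and the protocol promises the number. The gap is that the SAP, which specifies the outputs, does not include it. The SAP cites Protocol Version 8.2AB and the protocol supplied is Version 10. The sentence in 6.6 is not marked as new text in Version 10, but whether it stood in 8.2AB cannot be checked here.

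Second, low counts that changed dosing are counted. Protocol 5.3.5.4 makes them AEs, and SAP 4.11.3 tabulates AEs leading to interruption and to discontinuation. This also stands, and it limits the gap to low counts that met none of the AE criteria.

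Third, a reader might infer that the monitoring rule itself clears transient lows out of the endpoint value. In the middle bands of Tables 2 and 3, interruption applies only when the low count persists, so a brief dip does not trigger it.

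Fourth, the remark that decreases were mostly transient comes from the completed double-blind periods. It does not show that the SAP authors disregarded a known pattern. It does show that the pattern is one an endpoint table describes poorly.

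Finally, a reader might call the Appendix 7.5 limit, "change from baseline of at least the designated amount during or within 30 days after end of trial treatment", an error because Withdrawal Visit tests are aimed at 12 weeks after the last dose. Whether off-drug values belong in such a criterion is a matter of judgement, and it has no bearing on low counts during treatment.

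**Conclusion.** The point holds as a mismatch between protocol and SAP and as a weak choice of summary. The SAP omits the marked-abnormality count that Protocol 6.6 promises, and no laboratory table it commits to counts, by arm, patients who ever had low neutrophils or platelets. Low counts recorded as AEs are still tabulated.

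The size depends on how the undefined endpoint value is read. If it is the last value, about 8% (one draw) to 23% (three draws) of affected patients would appear in the shift table with 13 draws. Episode length, random timing and one episode per patient are assumptions. The documents give no double-blind rate of low counts by arm, so no number of missed patients can be derived from them.

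**What to change.** In SAP 4.11.10:

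1. Base the shift tables on the worst post-baseline value in the double-blind period, including unscheduled results: the lowest value for neutrophils and platelets. If an endpoint shift is kept as well, define the endpoint value.
2. Add the number and percentage of patients by arm with any marked abnormality, as Protocol 6.6 states.
3. Add the number and percentage of patients by arm according to lowest neutrophil count (above 1,000, 500–1,000, below 500/µL) and lowest platelet count (above 75,000, 50,000–75,000, below 50,000/µL). These are the existing cut points of Protocol Tables 2 and 3, used only as reporting categories; no dosing rule changes.

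The cost is some SAP wording and a few extra tables from data already collected. The downside is that the abnormality counts will look less favourable than an endpoint table, in both arms.

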>5x ULN	
Laboratory tests (ALT, AST, ALP, and TBL) should be repeated within 72 hours as soon as possible to confirm value. If continued, satralizumab should be discontinued immediately and gastroenterology expert should be contacted.
 
The presence of clinical symptoms should be queried. Patients who are far away from the trial site may be retested locally if prompt return to the trial site is difficult.

ALP= alkaline phosphatase; ALT = alanine aminotransferase; AST = aspartate aminotransferase; INR= international normalized ratio; TBL= total bilirubin; ULN= upper limit of normal.

* ULN or patient's baseline whichever is higher.

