4.11.12 Electrocardiograms

For quantitative ECG measurements (heart rate, PR interval, ORS duration, OT interval, and corrected QT intervals using Bazett and Fridericia correction methods), values during the double-blind period will be presented by treatment group for all visits.

The Bazett corrected QT (QTcB) will be calculated as

QTcB=QT/RR $^{0.5}$, where RR = 60/HR.

The Fridericia corrected OT (OTcF) will be calculated as

QTcF=QT/RR $^{0.33}$, where RR = 60/HR.

TP-GDO-WW-016-01 Confidential Version 7.0 Effective Date: 28Aug13 Version Date: 28NOV2018 Related to: SOP-GDO-WW-019

The following summaries and listings will be provided for the SAF and all SA237:

- A summary of 12-lead by treatment group at each specified visit.
- The number and percentage of subjects with a QTc (using Bazett and Fridericia corrected) of ≤450ms, >450 to ≤480ms, >480 to ≤500ms, and >500ms will be summarized by treatment group at each specified visit.
- The number and percentage of subjects with a QTc (using Bazett and Fridericia corrected) of an increase from baseline of >0 to ≤30ms, >30 to ≤60ms, and >60ms will be summarized by treatment group at each specified visit.
- The number and percentage of subjects with PR interval values ≤120ms, >120 to ≤220ms, and >220ms, and the number and percentage of subjects with QRS interval values ≤60ms, >60 to ≤120ms, and >120ms will be presented by treatment group at each specified visit.
- A summary of incidence of treatment-emergent abnormality 12-lead ECG findings after start of study drug by treatment group.
- A by-subject listing of abnormal 12-lead ECG data will be provided.

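### The AST/ALT bands in SAP 4.11.11 leave maxima strictly between 5 and 6, 10 and 11, and 20 and 21 times ULN in no row of that table

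*SAP*

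**What the plan says.** SAP section 4.11.11 (AST and ALT) defines the bands as follows: "AST and ALT will be categorized into four group (>3-5 xULN, 6-10 xULN, 11-20 xULN and 21- xULN"). Each subject is placed "based on maximum post-baseline levels within baseline and post-baseline respectively for each test", and the bands are crossed with categories of total bilirubin and alkaline phosphatase.

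Two further rules apply:

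- Subjects with results "fulfilling criteria for more than one category are counted only once, in the category indicating the highest elevation level" reached.
- "The denominator is the number of subjects with any valid assessment at baseline and post-baseline respectively".

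The section has no rule for rounding the multiple of ULN, no row for values that meet none of the bands, and no row for values at or below 3 times ULN.

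Protocol section 5.1.1.4, Table 4, divides the same scale without a break. One row covers >3 to 5x ULN and the next covers everything >5x ULN. The second row carries its own instruction: "If continued, satralizumab should be discontinued immediately and gastroenterology expert should be contacted".

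**The concern.** The bands are written as if multiples of ULN were whole numbers, but a laboratory value divided by its upper limit need not be one. A peak of 5.5, 10.5 or 20.5 times ULN satisfies none of the four definitions. Because the denominator is everyone with a valid assessment, such a subject is not shown as missing. In the table the subject looks the same as someone who never exceeded 3 times ULN.

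The first gap matters most. It opens immediately above 5 times ULN, where the protocol's own hepatic table changes row. A reader who adds the upper three rows to count subjects above 5 times ULN would get too low a number whenever a peak fell in a gap.

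**Working it through.** **1. Apply the bands as written.** They are (3, 5], [6, 10], [11, 20] and [21, ∞) times ULN.

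| Maximum (xULN) | Band as written | Contiguous band |
|---|---|---|
| 5 | >3-5 | >3 to ≤5 |
| 5.01, 5.5, 5.99 | none | >5 to ≤10 |
| 6, 10 | 6-10 | >5 to ≤10 |
| 10.5 | none | >10 to ≤20 |
| 11, 20 | 11-20 | >10 to ≤20 |
| 20.5 | none | >20 |
| 21 | 21 and above | >20 |

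The gaps are the open intervals (5, 6), (10, 11) and (20, 21). Their whole-number end points are covered.

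**2. Express the gaps in laboratory units.** Section 4.11.11 does not name the source of the ULN, so the reference limits in SAP Appendix 7.5 are used here for illustration. A gap runs from just above k × ULN to just below (k + 1) × ULN, for k = 5, 10 and 20. For ALT in men, 5 × 55 = 275 and 6 × 55 = 330, so whole-number values 276 to 329 U/L are unassigned.

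| Test (ULN, U/L) | 5-6 gap | 10-11 gap | 20-21 gap |
|---|---|---|---|
| ALT, men (55) | 276-329 | 551-604 | 1101-1154 |
| ALT, women (30) | 151-179 | 301-329 | 601-629 |
| AST, men (40) | 201-239 | 401-439 | 801-839 |
| AST, women (25) | 126-149 | 251-274 | 501-524 |

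With contiguous bands, no value above 3 times ULN is unassigned under any of the four limits.

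**3. Look for a rule that closes the gaps.**

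- The counting rule covers results that meet more than one band. It does not address a result that meets none.
- If the bands were applied result by result, a subject with 4 and then 5.5 times ULN would be counted in the >3-5 row, which is too low.
- Rounding to the nearest whole multiple would put 5.01-5.49 in the >3-5 row and would drop 3.01-3.49 altogether, since these round to 3, which is not above 3.
- Rounding up would give exactly the contiguous bands: 3.01 becomes 4, 5.01 becomes 6, 10.01 becomes 11 and 20.01 becomes 21. That may be what was intended, but the SAP does not say so.

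**4. Compare with practice elsewhere in the documents.** The SAP's QTc bands in section 4.11.12 have no breaks: ">450 to ≤480ms, >480 to ≤500ms, and >500ms". Protocol Table 4 has none either.

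**5. Size.** The documents give no count of patients above 3 times ULN and no distribution of peaks. Protocol section 5.1.1.4 says only that most elevations in the Phase 3 studies were below 5 times ULN. What can be computed is the weight of one missed patient. With 90 patients randomized 2:1, the planned arms are 60 and 30. If all have a valid post-baseline assessment, one patient is 1/60 = 1.7 percentage points on satralizumab and 1/30 = 3.3 on placebo.

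**The case against.** The strongest reply is that nobody is lost from safety reporting. Much of that is right:

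- SAP section 4.11.10 provides a by-subject listing of all laboratory data, in which "Values outside the normal range will be flagged within the listing", and a listing of treatment-emergent marked abnormalities.
- Under Appendix 7.5, a marked abnormality is ALT above 110 U/L or AST above 80 U/L with a rise of at least 50%, during treatment or within 30 days after it. On the male reference scale these limits are 110/55 = 2 and 80/40 = 2 times ULN, so every gap value exceeds them.
- A peak above 5 times ULN also meets the 50% rise if baseline was no more than 5/1.5 = 3.3 times ULN. Screening excludes patients above 1.5 times ULN.
- Protocol section 6.6 promises counts of patients meeting the marked-abnormality criteria.
- ALT or AST above 3 times ULN with bilirubin above 2 times ULN or jaundice is reported as an SAE or a non-serious AESI (Protocol 5.3.5.6). SAP 4.11.6 lists AESIs by subject.

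So a reader might infer that patients with marked elevations disappear from the trial's liver-safety reporting, and the documents do not support that. What the reply does not do is repair the table. A marked-abnormality count starting at 2 times ULN does not separate 4 from 5.5, and listings are not counts by band.

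A reader might also infer that the table is faulty because a transaminase maximum and a bilirubin maximum may come from different dates. The documents do not support that as an error. Crossing maxima is stated openly, and a column definition such as "total bilirubin > 2xULN and alkaline phosphatase <= 5xULN" says nothing about timing. For transaminase against bilirubin, crossing maxima is a sensitive screen: it can over-include, but it cannot miss a subject whose two values were raised together. Same-sample pairing would be a preference.

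**Conclusion.** The point holds as a boundary error in one descriptive table, and it is minor. Maxima in the three open intervals are counted in no band while the subject remains in the denominator, so the table can only understate elevations. This rests on reading the multiple of ULN as continuous. The strict >3 at the start of the first band suggests that reading, and nothing in the SAP contradicts it.

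The error does not touch the primary or key secondary analyses, eligibility, or the handling of raised transaminases at the site, which depends on individual results.

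A reader might want to attach a percentage of patients lost. That needs an assumed shape for the distribution of peaks and a base count above 3 times ULN. The documents give neither, so no share is offered here. The number may be zero, and the protocol's remark that most elevations were below 5 times ULN suggests that it is small.

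**What to change.** In SAP 4.11.11, replace the four bands with >3 to ≤5, >5 to ≤10, >10 to ≤20 and >20 xULN. Every maximum above 3 times ULN then falls in exactly one row, and the 5-fold cut matches Protocol Table 4. The bilirubin and alkaline phosphatase cross-classification need not change for this purpose.

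The cost is one line of SAP text and the matching change to the table code. No new data are needed.
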